### List of Abbreviations

AE	Adverse event
ANCOVA	Analysis of covariance
ADA	Anti-drug antibody
ATC	Anatomical Therapeutic Chemical Classification System
BMI	Body mass index
BP	Bodily Pain
CBC	Complete blood count
CMH	Cochran-Mantel-Haenszel
CRF	Case Report Form
CRO	Contract Research Organization
CSI	Composite Score of Interest
CSR	Clinical study report
CTCAE	Common Terminology Criteria for Adverse Events
ECG	Electrocardiogram
eCRF	Electronic Case Report Form
EDC	Electronic Data Capture (system)
EG	Eosinophilic gastritis
EGD	Esophago-gastro-duodenoscopy
EGE	Eosinophilic gastroenteritis
EGID	Eosinophilic gastrointestinal disorders
EoE	Eosinophilic esophagitis
ET	Early Termination
FDA	Food and Drug Administration
FSH	Follicle-Stimulating Hormone
GH	General Health
HPF	High power field
ICH	International Conference on Harmonization
ICF	Informed Consent Form
IV	Intravenous
MCS	Mental Component Summary
MedDRA	Medical Dictionary for Regulatory Activities
MITT	Modified Intention-to-Treat (population)
MH	Mental Health
MMRM	Mixed Model for Repeated Measures

---

PCS	Physical Component Summary
PD	Pharmacodynamics
PID	Patient Identification (number)
PE	Physical examination
PF	Physical Functioning
PK	Pharmacokinetic(s)
PT	Preferred term
PRO	Patient-reported outcome
p-value	Probability value
QoL	Quality of Life
RE	Role-Emotional
RP	Role-Physical
SAE	Serious adverse event
SD	Standard deviation
SAP	Statistical Analysis Plan
SF	Social Functioning
[REDACTED]	[REDACTED]
SOC	System organ class
TEAE	Treatment-emergent adverse event
TEAESI	Treatment-emergent adverse event of significant interest
TESAE	Treatment-emergent serious adverse event
TLF	Tables, Listings, and Figures
TSS	Total Symptom Score
VT	Vitality
WHO	World Health Organization
WHODD	World Health Organization Drug Dictionary

## Revision History

Version Date	Version Number	Description
28 Aug 2018	1	First version of the Statistical Analysis Plan
29 May 2019	2	

1. Updated to match with the protocol amendment 6

2. Clarified how the “14 days following last dose/2 weeks prior to biopsy” for PRO CFB analysis is defined

3. Removed ITT population

4. Added Treatment Responder as the 1st secondary endpoint and classified TSS as the 2nd secondary endpoint

5. Removed previous 7.10.3 Sensitivity Analysis 2 with missing data imputed based on MNAR assumption and Sensitivity Analysis 3 using log-transformed data for the primary endpoint

6. Removed previous 7.10.4 Subgroup Analysis for the primary endpoint

7. Replaced “change from baseline” with “percent change from baseline” for the secondary endpoints

8. Clarified 7.11.1 for how % change in TSS at end of treatment is calculated. Replaced MMRM with ANCOVA. Removed sensitivity analysis with missing data imputation

9. Added subgroup analysis for the 1st secondary endpoint

10. Expanded Exploratory Endpoints to include [REDACTED] for the [REDACTED], and [REDACTED] [REDACTED]

11. Revised the language for the ADA analysis.

## 1. Introduction

This statistical analysis plan (SAP) describes the rules and conventions to be used in the analysis and presentation of efficacy, safety, tolerability, and pharmacodynamic data as planned for the clinical protocol. It describes the data and variables to be summarized or analyzed, including specifications of the analytical methods to be performed. The SAP presented in this document supersedes the statistical analysis methods described in the clinical protocol. Significant deviations/changes from the planned analyses described in this SAP will be identified, with justification, in the appropriate section of the clinical study report (CSR). This SAP is based on the clinical study protocol AK002-003 Amendment 6, dated 07 February 2019, and its associated electronic case report forms (eCRF).

## 2. Study Objectives

### 2.1 Primary Objective

The primary objectives of the study are to evaluate:

- 1) The efficacy of AK002 in patients with EG and/or EGE as estimated by the number of eosinophils per HPF in gastric biopsies before and after receiving AK002 or placebo.
- 2) The safety and tolerability of AK002 in patients with EG and/or EGE.

### 2.2 Secondary Objectives

The secondary objectives are to evaluate preliminarily the effects of AK002 in patients with EG and/or EGE by comparing AK002 to placebo treatment for the following parameters:

- 1) Compare treatment responders between AK002 and placebo; a responder is a patient who exhibit a >30% reduction in Total Symptom Score (TSS) (all PRO symptoms) and a >75% reduction in mucosal eosinophils.
- 2) Changes in EG/EGE symptoms in a Patient Reported Outcome (PRO) questionnaire.

### 2.3 Exploratory Objectives

The exploratory objectives are to evaluate the effect of AK002 in patients with EG and/or EGE by comparing AK002 to placebo treatment for the following parameters:

- 1) Change in [REDACTED].
- 2) Changes in [REDACTED] in a Patient Reported Outcome (PRO) questionnaire.
- 3) Number of [REDACTED] in patients with [REDACTED]  
[REDACTED].
- 4) [REDACTED] before and after treatment.
- 5) Change in [REDACTED], respectively.

- 6) Change in [REDACTED]
- 7) Change in [REDACTED] and [REDACTED]  
[REDACTED]
- 8) Scoring of [REDACTED] using the [REDACTED]  
[REDACTED]

## 2.4 Safety Objectives

To evaluate the safety and tolerability of AK002 in patients with EG and/or EGE by determining AE incidence and severity, study withdrawals due to AEs, changes in vital signs and laboratory tests including immunogenicity, changes in concomitant medication use due to AEs, and other safety parameters.

## 3. Study Design

### 3.1 General Description

This is a Phase 2, multi-center, randomized, double-blind, placebo-controlled study. The study comprises a screening period of 21 to 35 days with baseline evaluations for study eligibility. If subjects meet histology and symptom eligibility criteria, they will receive 4 doses of AK002 or placebo by IV infusion on Days 1, 29, 57, and 85. Subjects will be followed for 56 days after last dose. Follow-up visits will occur on Days 113 and 141.

If the absolute lymphocyte or eosinophil counts have not recovered by Day 141, the follow-up period will be extended, and subjects will be followed until the counts have recovered. During the extended follow-up period, subjects will return to the site every 28 days for a follow-up safety visit.

Total study duration will be up to approximately 23–25 weeks.

The study design is presented schematically in [Table 1](#).

**Table 1 Schedule of Assessments**

Assessments	Visits										Extended Follow-up (if needed)
	Screening (Up to 5 Weeks)	Treatment Period (12 Weeks)						Post-Treatment Follow-up Period (8 Weeks)			
		Baseline 	Day 1 	Day 4 (±1 day)	Day 15 (±2 days)	Day 29 (±3 days)	Day 57 (±3 days)	Day 85 (±3 days)	Day 99 (±3 days)	Day 113 (±3 days)	Day 141 (±3 days) or ET 
Informed consent	X										
Demographics	X										
Medical History	X	X									
Prior/concomitant Medications	X	X		X	X	X	X	X	X	X	
Body weight and height 	X	X		X	X	X			X	X	
Vital Signs 	X	X		X	X	X			X	X	
12-lead ECG 	X										
Complete Physical Examination 	X										
Baseline Diet Assessment 	X										
Baseline Diet Compliance 		X		X	X	X	X	X	X	X	
Stool for Ova and Parasite 	X										
ePRO Activation and Training 	X										
ePRO Questionnaire 	<----- Perform DAILY from Screening through Day 141 or 28 days after last dose if ET ----->										
██████████ 	X	X (pre-dose)			X (pre-dose)	X (pre-dose)	X (pre-dose)		X	X	
EGD with Biopsy 	X								X		
██████████ 	X								X		
Serum Pregnancy test & FSH 	X										
Urine Pregnancy test 		X (pre-dose)			X (pre-dose)	X (pre-dose)	X (pre-dose)			X	
Eligibility Assessment	X	X									
Stratification and Randomization 		X (pre-dose)									
Access IRT-enter PID and subject weight		X (pre-dose)			X (pre-dose)	X (pre-dose)	X (pre-dose)				
Access IRT for first subject screened to trigger first IP shipment	X										

**Table 1** Schedule of Assessments cont.

Assessments	Visits										Extended Follow-up (if needed)
	Screening (Up to 5 Weeks)	Treatment Period (12 Weeks)						Post-Treatment Follow-up Period (8 Weeks)			
Assessments	Baseline 	Day 1 	Day 4 (±1 day)	Day 15 (±2 days)	Day 29 (±3 days)	Day 57 (±3 days)	Day 85 (±3 days)	Day 99 (±3 days)	Day 113 (±3 days)	Day 141 (±3 days) or ET 	Every 28 Days  (±3 days)
Premedication with cetirizine and acetaminophen or approved alternative 		X (pre-dose)			X (pre-dose)	X (pre-dose)	X (pre-dose)				
Study drug administration 		X			X	X	X				
Symptom-directed Physical Exam 		X		X	X	X	X		X	X	
CBC with differential 	X	X	X	X	X	X	X	X	X	X	X
Chemistry 	X	X (pre-dose)		X	X (pre-dose)	X (pre-dose)	X (pre-dose)		X	X	
Urinalysis 	X	X (pre-dose)			X (pre-dose)	X (pre-dose)	X (pre-dose)		X	X	
Serology 	X										
Blood for exploratory safety analysis (if indicated) 		X			X	X	X				
Blood for histamine and tryptase (if indicated) 		X			X	X	X				
Blood for PK and storage 	X			X	X (pre-dose)	X (pre-dose)	X (pre-dose)		X	X	
Blood for Exploratory Analysis 		X (pre-dose)			X (pre-dose)		X (pre-dose)			X	
Blood for ADA 	X			X	X (pre-dose)	X (pre-dose)	X (pre-dose)			X	
Blood for Total Serum IgE 		X (pre-dose)								X	
Non-serious Adverse Events		X		X	X	X	X	X	X	X	
Adverse Events of Special Interest		X		X	X	X	X	X	X	X	X
Serious Adverse Events 	X	X		X	X	X	X	X	X	X	X
Begin AK002-003X extension study (if applicable) 									X		

ADA: Anti-AK002 antibody

ET: Early Termination

CBC: Complete blood count

FSH: Follicle-stimulating hormone

ECG: Electrocardiogram

Allakos, Inc.

**Table 1 Notes**

- 1) Baseline screening visit can occur over several days within the screening period. Day 1 can begin as soon as eligibility criteria are met.
- 2) At screening, height (in cm) and weight (in kg) will be recorded. Body weight will also be measured on Days 1, 15, 29, 57, 85, and on follow-up Days 113 and 141 or ET.
- 3) Vital signs will be measured at screening, Days 15, 99, 113, 141 or ET and on all dosing days pre-dose, 15 minutes ( $\pm 5$  minutes) after the start of study drug infusion, immediately following the end of infusion on treatment days (+5 minutes), 1 hour ( $\pm 15$  minutes) into the post-infusion observation period and just prior to discharge. Vital signs including systolic and diastolic blood pressure, pulse, body temperature, and respiratory rate will be measured after the subject has been at rest for  $>5$  minutes and before any blood draw.
- 4) An ECG will be obtained at screening before any blood is drawn and after the subject has been in the supine position for  $\geq 5$  minutes.
- 5) A complete physical examination will be performed by either the Investigator or designee and include the following body system or organ assessments: skin; head, eyes, ears, nose and throat; thyroid; lungs; cardiovascular; abdomen; extremities; lymph nodes; and a brief neurological examination.
- 6) A Baseline Diet Assessment will be performed using standardized questions. Eating patterns, food avoidance behaviors, and allergies will be captured.
- 7) A Baseline Diet Compliance check will be performed and any variances from the baseline diet documented. Subjects should try to maintain the baseline diet as much as possible throughout the study.
- 8) Fecal collection kits for Ova and Parasite test will be provided to subjects at screening. Collection kits should be returned to the clinical site within 1 day of collection.
- 9) Activate EG/EGE PRO questionnaire and provide subject with unique username and password. EG/EGE PRO questionnaire should be activated for all subjects. Subjects with concomitant history of atopic asthma, atopic dermatitis and/or eosinophilic esophagitis will receive an extra question, about each, as appropriate.
- 10) EG/EGE PRO should be completed around the same time each day. Prior to enrollment, the EG/EGE PRO weekly averages over the screening period will be calculated and used to assess eligibility and establish the baseline severity of symptoms.
- 11) To be completed by subject, in clinic, prior to any blood draw, physical exam, or vital sign measurements.
- 12) Specimen processed by central lab. See central laboratory manual for collection and processing details.
- 13) See Protocol Appendix 5 for biopsy assessments. The post-treatment endoscopy (EGD) and biopsy assessments will be performed on Day 99 ( $\pm 3$ ) and biopsy results will be blinded.
- 14) To be performed during the conduct of the EGD during the screening period and on D99.
- 15) Blood for serum pregnancy and FSH will be collected on screening, for subjects of childbearing ability or to show post-menopausal status.
- 16) Urine for urine pregnancy test will be collected pre-dose on all infusion days and at EOS. Test kits will be supplied by the central lab. Tests will be completed on site and evaluated prior to infusion(s).
- 17) Stratification based on highest weekly symptom average recorded (group of 3.0–4.9 or 5.0–10.0). Randomization and stratification will occur through Cenduit IRT.
- 18) Premedication required prior to first and second infusions and at the Investigator's discretion for third and fourth infusions, depending on tolerance of prior infusions.

- 19) Study drug will be administered as a single peripheral IV infusion over at least 5 hours on study Day 1 and at least 4 hours on Day 29 ( $\pm 3$  days) and Day 57 ( $\pm 3$  days). The infusion may be shortened to 3–5 hours for Day 85 ( $\pm 3$  days). Please refer to the Pharmacy Manual for detailed instructions on study drug preparations, administration, and infusion rates. Infusion must be completed within 8 hours of preparation of study drug.
- 20) A symptom-directed PE (including assessment of possible infusion site reactions) will be performed by the Investigator or designee, as needed if any symptoms are reported.
- 21) Blood for CBC with differential, including absolute [REDACTED] and basophil counts, will be obtained just prior to each infusion, 1 hour after the end of each infusion, 4 hours after the end of infusion 1, as well as during the screening period and on Days 4, 15, 99, 113, and 141 or ET and Extended Follow-Up, if applicable. All differential blood counts from Day 1 (post-dose) and prior to Day 141 or Early Termination will be blinded to the Sponsor and the site. An unscheduled CBC may be collected at the request of the unblinded safety monitor. Differential blood counts will not be blinded at the Day 141/ET visit and these results will be used by the site to determine if the subject needs to enter the Extended Follow-Up period.
- 22) Blood for chemistry will be obtained pre-dose on dosing Days 1, 29, 57, and 85, as well as during the screening period and on Day 15, Day 113, and Day 141 or ET.
- 23) Urine for standard urinalysis will be obtained pre-dose on dosing Days 1, 29, 57, and 85, as well as during the screening period and on Day 113 and Day 141 or ET.
- 24) Serology will include HBsAg, hepatitis C antibody, anti-HBc, and HIV.
- 25) If an Infusion-related reaction causes an infusion interruption or cessation a sample of blood should be obtained for exploratory safety analysis within 1–2 hours of the onset of the symptoms. A sample of blood should be obtained for testing of histamine and tryptase levels within 1–2 hours, if anaphylaxis is suspected.
- 26) Blood for PK should be obtained pre-dose on dosing Days 29, 57, and 85, as well as during screening and on Days 15, 113, and 141 or ET.
- 27) Blood samples for exploratory analysis will be collected pre-dose on Days 1, 29, and 85 and also on Day 141 or ET.
- 28) Blood samples for ADA will be collected during the screening period, on Days 15, 29, 57, 85 and Day 141 or ET and anytime an immunogenicity-related AE occurs.
- 29) Blood samples for Total Serum IgE will be collected on Day 1 and on Day 141 or ET.
- 30) The ET Visit should be conducted 28 ( $\pm 3$ ) days after the last dose of study drug or prior to this, if necessary, to ensure compliance with the visit. If early termination occurs more than 28 days after the last dose of study drug, then perform the ET visit as soon as possible. The procedures listed under the final follow-up visit will be conducted unless directed otherwise by the Medical Monitor.
- 31) The reporting of Serious Adverse Events occurring after signing Informed consent and prior to the first infusion will be limited to those that relate to screening procedures. The capture of all other SAEs and Adverse Events that are not SAEs will begin at the time of first infusion of study drug.
- 32) Extended follow-up, if needed, every 28 days ( $\pm 3$  days) until eosinophil and/or lymphocyte counts have recovered.
- 33) Subjects who sign the informed consent for the AK002-003X extension study will complete the procedures for Day 113 and then immediately begin open-label dosing in the extension study if eligible. Subjects will not complete the Day 141 procedures or extended follow-up under the AK002-003 protocol. Open-label dosing and follow-up including any extended follow-up required to monitor the recovery of lymphocytes and eosinophils will occur under the AK002-003X extension protocol.

### **3.2 Study Treatment**

#### **3.2.1 Treatment, Dose, and Mode of Administration**

- Treatment Group 1: 0.3 mg/kg AK002 on Day 1 followed by 1 mg/kg on Day 29, followed by 3 mg/kg on Days 57, and 85
- Treatment Group 2: 0.3 mg/kg AK002 on Day 1 followed by 1 mg/kg on Days 29, 57, and 85
- Treatment Group 3: Placebo on Days 1, 29, 57, and 85

#### **3.2.2 Duration of Study**

Total subject duration on study is approximately 23–25 weeks.

- Screening phase: 21–35 days
- Treatment phase: 85 days ( $\pm 3$  days)
- Follow-up after last dose: 56 for subjects who do not enroll in the AK002-003X extension study or 28 days ( $\pm 3$  days) for subjects who enroll in the AK002-003X extension study. If the absolute lymphocyte or eosinophil counts have not recovered by Day 141, the follow-up period will be extended, and subjects will be followed until the counts have recovered.

#### **3.2.3 Methods of Assigning Subjects to Treatment Group**

Approximately 60 subjects will be stratified based on the highest weekly average of the qualifying symptom of disease recorded on the PRO questionnaire during the screening period (PRO score 3–4.9, or 5.0–10.0) and randomized in a 1:1:1 ratio to Treatment Groups 1, 2, and 3 (Section 3.2.1).

### **3.3 Blinding**

This is a double-blind study. The identity of test and placebo treatments will not be known to investigators, sponsor, research staff, subjects, or the primary study monitor. Only the unblinded study pharmacist, the unblinded pharmacy monitor and the unblinded safety monitor will know the treatment assignment.

### **3.4 Hypotheses**

The hypothesis to be tested in the study is that AK002, in either one or both of the 2 doses, are different from placebo with regard to the primary endpoint of number of eosinophils per HPF in biopsies from the gastric mucosa.

### 3.5 Determination of Sample Size

Assuming a reduction of 30% in the number of eosinophils per HPF (primary endpoint) from baseline in the AK002-treated group (Treatment Group 1 or 2) versus a 10% reduction per HPF in the placebo group (Treatment Group 3), and assuming a standard deviation of 20%, 20 subjects per group would provide 87% power with a significance level of 0.05.

### 3.6 Changes to Analyses Planned in the Protocol

The protocol-defined gatekeeping procedure of high dose then low dose comparison to placebo for the primary endpoint is revised to include high/low pooled, high, and low dose comparisons to placebo for the primary and secondary endpoints.

The protocol-defined treatment responder is now classified as the 1st secondary endpoint and percent change from baseline to end of treatment in TSS is now the second (2nd) secondary endpoint. Other protocol-defined secondary endpoints are now moved to the exploratory endpoints.

The protocol-defined MITT population is now replaced with Per Protocol population for efficacy analysis.

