## **6.8 Multiple Comparisons/Multiplicity Adjustment**

To control for the family-wise type-I error rate, the following testing procedures will be implemented:

1. Test the high/low dose (Treatment Groups 1 and 2) combined group against placebo (Treatment Group 3) for the primary efficacy endpoint. If  $p \leq 0.05$  then proceed to
2. Test the high/low dose combined group against placebo for the 1st secondary efficacy endpoint. If  $p \leq 0.05$  then proceed to
3. Test the high/low dose combined group against placebo for the 2nd secondary efficacy endpoint. If  $p \leq 0.05$  then proceed to
4. Test the high dose against placebo for the primary efficacy endpoint. If  $p \leq 0.05$  then proceed to

5. Test the low dose against placebo for the primary efficacy endpoint. If  $p \leq 0.05$  then proceed to
6. Repeat above Steps 4-5 for testing the 1st secondary efficacy endpoint, then the 2nd secondary efficacy endpoint.

In the above sequential testing, if any step has  $p > 0.05$  then the tests of this step and of all subsequent steps will be considered not statistically significant.

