#### 7.1.2 Per Protocol Analysis (PP) population

The per protocol population will include all randomized subjects who do not have major protocol deviations adversely affecting the data interpretation. Some examples of PP exclusion criteria are

- Did not receive at least 2 doses of study medication
- Changed dose of systemic steroids and/or started systemic steroid treatment during the study or injections of steroids in the stomach and/or duodenum (this does not include steroids used as premedication the day before and/or the day of study drug infusions).
- Received other prohibited medications (eg, IL-5 inhibitors, dupilumab) potentially impacting efficacy during study treatment

- Did not have at least 6 PROs over 14 day period at any timepoint after administration of second dose.

The study statistician along with the study team will review protocol deviations to identify subjects to be excluded from the per protocol analysis population. The PP exclusion criteria will be updated prior to the database lock and unblinding. The PP population will be specified prior to unblinding using said exclusion criteria.

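### Per Protocol is the only efficacy population, so no Section 6.8 test has a planned result in all randomised or all treated subjects, not even as a sensitivity analysis

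*SAP*

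**What the plan says.** SAP Section 3.6 makes the change in one sentence, without a reason: "The protocol-defined MITT population is now replaced with Per Protocol population for efficacy analysis". The revision history for version 2 also records the removal of the ITT population.

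Section 7.1 leaves two sets wider than PP. All enrolled subjects are used for disposition (Section 7.2). The Safety population is used for safety endpoints, exposure, medications and baseline tables. Neither is given an efficacy analysis.

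The test sequence opens with "Test the high/low dose (Treatment Groups 1 and 2) combined group against placebo (Treatment Group 3) for the primary efficacy endpoint" (Section 6.8). Neither that section nor Sections 7.10 and 7.11 name a population, so Section 3.6 governs them all.

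Section 7.1.2 introduces its list with "Some examples of PP exclusion criteria are" and gives four:

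- On dosing, the first criterion reads: "Did not receive at least 2 doses of study medication"
- On steroids, the second reads: "Changed dose of systemic steroids and/or started systemic steroid treatment during the study" (or steroid injections in the stomach or duodenum; premedication is exempt)
- On other drugs, the third reads: "Received other prohibited medications (eg, IL-5 inhibitors, dupilumab) potentially impacting efficacy during study treatment"
- On diaries, the fourth reads: "Did not have at least 6 PROs over 14 day period at any timepoint after administration of second dose"

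It adds: "The PP exclusion criteria will be updated prior to the database lock and unblinding". Membership of PP is to be specified before unblinding.

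**The concern.** Each listed exclusion depends on something that happens after randomisation. Stopping before a second dose may reflect poor tolerability or lack of benefit. Starting steroids or another active drug may itself be a sign of treatment failure, yet it removes the subject instead of counting against the arm. Missing diaries may go with worse health or lower engagement. If exclusion differs by arm and is related to outcome, the groups being compared are no longer the randomised groups, and the estimate is biased in a direction that cannot be known in advance.

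This reaches the first test and every later step of a sequence that Section 6.8 presents as controlling the family-wise type I error. The tables in Sections 7.2 to 7.4 would show that exclusion was unequal. They would not show whether the efficacy result holds when the excluded subjects are put back, and any such analysis added later would be post hoc.

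**Working it through.** **Is a wider efficacy analysis planned anywhere?** The candidates are:

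- Section 7.10.2 (CMH row-mean-score test) changes the method and names no population.
- Section 7.10.3 counts a missing eosinophil count as non-response. It names no wider set, uses another endpoint (below 30 cells/HPF) and is not a Section 6.8 step. Under Section 3.6 it reaches only subjects still in PP.
- Sections 7.11.1 and 7.11.2 name no population. The revision history records that the missing-data sensitivity analysis for TSS was removed.

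None fills the gap.

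**Reproducing the plan's figure.** Inputs from Section 3.5: reductions of 30% and 10% (difference 20 points), SD 20, 20 per group, alpha 0.05 (taken as two-sided). The noncentrality is 20/(20·√(1/20+1/20)) = 3.16 on 38 df, and power is 86.9%, against the stated 87%.

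**Possible size of the bias.** The SAP gives no exclusion rate, so these are assumed scenarios. There is no true effect (mean change −10 in both arms), SD is 20, and 40 pooled active subjects are compared with 20 on placebo. A subject is excluded when a latent score, with correlation ρ to worse outcome, passes a threshold set by the exclusion rate. There were 200,000 runs per scenario (simulation SE about 0.05 percentage points at 5%). The ANCOVA adjusts for baseline (assumed correlation 0.3 with outcome) and a 50:50 stratum. A negative shift favours active.

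| Excluded (active / placebo) | Type I error, t-test, ρ = 0.3 / 0.5 | Type I error, ANCOVA | Shift in points, t-test | Shift in points, ANCOVA |
|---|---|---|---|---|
| 10% / 0% | 5.47% / 6.66% | 5.46% / 6.40% | −1.14 / −1.94 | −1.05 / −1.77 |
| 0% / 10% | 5.33% / 5.93% | 5.25% / 5.81% | +1.17 / +1.95 | +1.06 / +1.78 |
| 15% / 5% | 5.42% / 6.19% | 5.39% / 6.05% | −1.01 / −1.66 | −0.92 / −1.52 |
| 10% / 10% | 4.98% / 4.95% | 4.98% / 4.96% | within 0.02 | within 0.02 |

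With no exclusion the rates are 5.05% (t-test) and 5.03% (ANCOVA). With ρ = 0, every scenario stays within about 0.1 point of 5% and shows no shift.

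Analytic check when one arm loses a fraction f: shift = SD·ρ·φ(c)/(1−f). At f = 10%, c = 1.2816 and φ(c) = 0.1755. This gives 20×0.3×0.1755/0.9 = 1.17 and 20×0.5×0.1755/0.9 = 1.95, in line with the table.

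**Responder endpoint, assumed counts.** Start from 16/40 against 4/20, a difference of 40.0 − 20.0 = 20.0 points.

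- Dropping 4 active non-responders: 16/36 − 4/20 = 24.4.
- Dropping 2 placebo non-responders: 16/40 − 4/18 = 17.8.
- Dropping both sets: 16/36 − 4/18 = 22.2.

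**Power if the fuller set became primary.** Section 3.5 inputs, with 10% of active subjects responding like placebo (200,000 runs for the third column, noncentral t for the others):

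| Comparison | All respond as planned | Those 10% excluded | Those 10% kept |
|---|---|---|---|
| Pooled vs placebo | 94.8% (40 v 20) | 94.1% (36 v 20) | 88.6% |
| One dose vs placebo | 86.9% (20 v 20) | 85.0% (18 v 20) | 78.0% |

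**The case against.** The strongest reply is that the harm is hypothetical. Inflation needs exclusion that is both unequal and related to outcome, and nothing in the SAP shows that it will be. Milder imbalance does less: in a 100,000-run t-test simulation, 10% active and 5% placebo gives 5.0% / 5.4% with a shift of 0.5 / 0.9 points, and 5% active only gives 5.2% / 5.6% with 0.6 / 1.1 points. Even 1.9 points is small beside the planned 20. This stands, and the size should not be overstated. Against it, the two-sided rate hides the direction: with 10% active-only exclusion, false results favouring active rise from 2.5% to 4.0% / 5.5%.

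A second reply is that subjects with fewer than two doses may have no post-treatment biopsy and would leave the ANCOVA in any population. Table 1 note 13 places that biopsy at Day 99, and note 30 mentions none at early termination. This is partly right, and the simulation does not allow for it. But Section 5.2 foresees biopsies after early discontinuation, and subjects excluded for steroids or prohibited drugs can have Day 99 data.

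Third, PP is fixed before unblinding, and exclusions are listed with reasons. That limits data-driven selection but does not restore the randomised comparison.

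Two smaller points also carry weight. Table 1 note 25 shows that infusions may be stopped for reactions, but it concerns blood sampling and does not say that later doses are withheld, so it is weak evidence of unequal dosing. And if the diary rule means no 14-day span with six diaries at any time after the second dose, it removes few subjects. It suits the TSS endpoints but has no bearing on a biopsy endpoint.

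Finally, this is a Phase 2 study of about 60 subjects, and making the fuller set primary may cost power. That bears on which set is primary, not on whether a fuller-set analysis should exist.

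**Conclusion.** The point holds. Section 3.6 makes PP the sole efficacy population, no other section restores a wider one, and every Section 6.8 test is run in subjects selected partly by events after randomisation. This reading rests on the text alone.

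The size is not established by the documents. Under the assumed one-sided or unequal exclusions, with correlation 0.3 to 0.5 with outcome, type I error is about 5.3% to 6.7% and the estimate shifts by roughly 1 to 2 points in either direction. With equal exclusion under the same rule there is no effect. The case rests on the missing check, which affects every confirmatory test and can be added cheaply before unblinding.

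**What to change.** 1. Run the Section 6.8 tests in all randomised subjects who received at least one dose, analysed as randomised, with PP as supportive. At the least, prespecify that analysis as a sensitivity analysis for the primary and both secondary endpoints. Name the population in Sections 6.8, 7.10 and 7.11.
2. In that set, count subjects with a missing biopsy or TSS as non-responders for the responder endpoint. For the two percent-change endpoints, use all available post-baseline data, including early-discontinuation biopsies, state how missing values are handled, and add one missing-data sensitivity analysis.
3. Replace the examples in Section 7.1.2 with a complete list before unblinding, and do not let the diary criterion remove a subject with a valid biopsy from the eosinophil endpoint.

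The cost is SAP wording and one more set of tables. As a sensitivity analysis, the fuller set costs no power. As the primary analysis it may be diluted: with 10% of active subjects placebo-like, power is 88.6% against 94.1% under PP for the pooled test, and 78.0% against 85.0% for a single dose, which affects steps 4 to 6. Item 1 in its sensitivity form is the minimum and can be adopted without the rest.
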